The proposed follow-up builds upon trials of other interventions and expands the list of outcomes to include state-of-the-art measures of obesity and fat distribution, arterial stiffness, CKD, metabolic outcomes, immune/inflammatory markers, and mortality—for both mothers and their firstborn offspring. By examining the impact of a comprehensive program of prenatal and infant/toddler home-visiting by nurses on maternal and offspring adult chronic-disease risk in an RCT, the current study holds considerable promise for addressing this critical public health challenge.

Sampling Design of Original Clinical Trial

Original Sample Characteristics. We invited 1,290 women from the obstetrical clinic of the Regional Medical Center in Memphis to participate (Table 1). We recruited women <29 weeks pregnant if they had no previous live births, no specific chronic illnesses thought to contribute to fetal growth retardation or preterm delivery, and at least 2 sociodemographic risks (unmarried, <12 years of education, unemployed). Eighty-eight percent (1138/1289) completed informed consent and were randomized to 1 of 4 treatment conditions.⁶³

Treatment Conditions

Table 1 summarizes services provided and numbers of participating families randomized into each of 4 treatment conditions in this trial. The study was designed to follow 742 families in 2 treatment conditions after delivery (Treatments 2 and 4). Details of the allocation procedures are found in our original publication.⁶³

Table 1. Services provided in each treatment condition

Services	Treatment 1 N=166	Treatment 2 N=514	Treatment 3 N=230	Treatment 4 N=228
Transportation for prenatal care	X	X	X	X
Screening and referral for children		X		X
Prenatal/postpartum home visiting			X	X
Infant and toddler home visiting				X

Treatment 1 - Transportation during Pregnancy. The 166 families in this treatment condition received free round-trip taxicab transportation for scheduled prenatal care appointments. This group did not receive any postpartum services or assessments (with the exception of maternal death records described below).

Treatment 2 - Transportation during Pregnancy and Screening during Infancy. The 514 families in this condition received: 1) free transportation for scheduled prenatal care; and 2) developmental screening and referral services for the child at the 6th, 12th, and 24th months of the child's life.

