Treatment 3 - Transportation and Nurse-Visitation during Pregnancy Only. The 230 families in this condition received: 1) free transportation for scheduled prenatal care; and 2) intensive nurse home-visitation services during pregnancy and one postpartum visit in the hospital before discharge and one postpartum visit in the home. This group did not receive any other postpartum services or assessments (except death records).

Treatment 4 - Transportation and Nurse-Visitation during Pregnancy and Infancy. The 228 families in this condition received: 1) free transportation for scheduled prenatal care; 2) intensive nurse home-visitation services during pregnancy and through the child's second birthday; and 3) developmental screening and referral services for the child at the 6th, 12th, and 24th months of the child's life.

Note that the trial was structured to follow Treatments 2 and 4 after delivery to minimize study costs, and these two groups have been followed through offspring age 18. In planning the current follow-up, we conducted pilot work and found that our success in tracing T1 and T3 participants would be significantly less

than those in T2 and T4, so we chose not to attempt to follow them.

Program Plan and Implementation

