signs, symptoms, health care provider diagnoses of chronic diseases, history, medications, surgeries, hospitalizations). Other components of the interview may be conducted by other trained study staff. Some of the measures consist of repeated measures of outcomes examined in earlier phases of the trial. Others, focusing on key behaviors for this phase of follow-up are new measures appropriate to the life stages of the participants and the outcomes being examined. These include measuring physical activity and sedentary activity levels which influence disease risk, dietary assessments, and the PSQI for measurement of sleep. The study staff will also collect information on use of substances, depression, anxiety, sense of mastery, duration and quality of partnered relationships, education, work, and incarceration. We will assess the availability and source of medical care. This information will be used to make judgements about referrals (addressed below) in light of abnormal physical assessments and lab results.

Sharing results of clinically relevant laboratory results and physical assessments with participants. We will share results of key physical health measurements at the time of assessment in the study office. Serious conditions reflective of imminent risk will be referred for emergency care (e.g. elevated BP). We will send the results of the clinically relevant urine and blood assays to subjects once results are analyzed, and encourage them to seek care if values exceed clinical cut-offs. If participants have no providers, we will refer them to their State Health Insurance program for help in gaining access to care.

All biological analyses will be done in the Medpace Reference Laboratories. Overview: The following will be analyzed: Lipid Profile (TC, HDL, LDLc, TG), Chemistry Panel (AST, ALT, Serum Albumin and Serum Creatinine), eGFR (calculation), ALT/AST ratio (calculation), HbA1c, Urine Albumin/Creatinine, FSH, hsCRP, Fibrinogen, IL-6, TNF-alpha receptor 2 and IGF-1 (total).

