We have hypothesized (H8) that NV effects on maternal primary outcomes will be mediated by earlier NV effects on the index of prenatal health behaviors, pregnancy outcomes (PIH in first births, preterm delivery), closely spaced subsequent pregnancies, sense of mastery, stable family structure following offspring birth, government benefit payments to the family, and hypertension at 12 and 18 years postpartum. We also have hypothesized (H9) that NV effects on offspring outcomes (H1-6) will be mediated, in part, by NV effects on the index of prenatal health behaviors, PIH, preterm delivery, breast feeding, maternal caregiving dysfunction (an index composed of maternal beliefs associated with child maltreatment and observed qualities of the home environment in the first 2 years of life), screen time at age 12, duration and quality of relationships, government benefit payments to the family, and obesity and prehypertension at ages 12 and 18.

Data from current participant interviews on sedentary and physical activity, sleep, diet, use of substances (especially cigarette smoking), depression, anxiety, sense of mastery, chronic pain, stable/supportive partnered relationships, educational achievement, paid employment, health insurance, and incarceration will be used as sources of data to explore other potential mediators of NV effects. Among offspring, we will gather reports of pregnancies and births since last interview dates. These sources of data will be explored as possible additional mediators on NV effects.

Statistical Models and Methods of Analysis

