The primary analyses will make use of general linear model methods and their extensions.⁸⁹⁻⁹⁴ The focus will be on (1) full model specification to account for all sources of variation, and full examination of interactions among model factors, including examination of homogeneity of regressions to understand interactions between classification effects and covariates; (2) generalized models to analyze dichotomous outcomes with binomial error distributions and count data assumed to have negative binomial distributions; (3) generalized linear mixed models (including repeated measures and growth-curve models) to account for correlated data and to examine differences in change over time; (4) semiparametric methods to model relations between variables without requiring a specific functional form;⁹⁵ (5) survival analyses including Kaplan-Meier, competing risks and Cox hazard models;⁹⁶⁻⁹⁹ (6) mediation analyses using structural equation models to examine causal processes, including the direct and indirect effects of treatment on outcomes.^{100,101}

The primary classification factors for examination in our models, as determined by our hypotheses and earlier work, include treatments (Control vs. Nurse Visited - T), maternal psychological resources (low versus high based on a median split – P), sex of offspring (S), and follow-up time (A) for outcomes assessed at multiple time points (e.g. obesity) – T|P|S and T|P|S|A. Covariates will be selected using a post-double-selection lasso (least absolute shrinkage and selection operator) procedure.¹⁰²⁻¹⁰⁴ This procedure will select covariates that are most related to intervention status (i.e. differences at randomization) or related to the dependent variable. Candidate covariates will include an index of household poverty, obesity, and maternal

pre-pregnancy BMI.

Statistical Power/Smallest Detectable Differences for Proposed Follow-Up

Given that sample size is fixed, we show below calculations of the smallest detectable treatment-control differences for the 29-year follow-up. Calculations for representative outcomes were carried out with the following assumptions: a Type I error of .05, Type II error of .20 (power of .80), 2-tailed tests, 10 percent of the variance accounted for by other terms in the model for normally distributed variables and N=600. Disproportionate sample sizes in Control and Nurse-Visited groups are taken into account.

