relationships, family economic resources, and hypertension at 12 and 18 years postpartum. H9: NV effects on offspring outcomes (H1-6) will be mediated, in part, by NV effects on prenatal health behaviors, preterm delivery, PIH, breast feeding, screen time at age 12, improved partner relationships, family economic resources through age 18, and obesity and prehypertension at ages 12 and 18. Tests of mediation will follow the empirical and theoretical model shown in Figures 1 and 2. We will employ mediation analyses using structural equation models to examine causal processes, including the direct and indirect effects of treatment on outcomes.^{100,101} To illustrate, we have hypothesized that NV will have an indirect effect on maternal arterial stiffness through its effect on PIH, preterm delivery, and the count of short inter-pregnancy intervals. To test one aspect of this hypothesis, we will regress maternal arterial stiffness on the count of closely spaced subsequent children (child density) within the control group; we also will regress child density on the treatment contrast. If the paths from the control sample to child density and from density to arterial stiffness are both significant, we will have met the joint significance test criterion. We will next calculate the indirect effect, based on these same two path coefficients, and compare the resultant z' to Mackinnon's table of critical values. If the z' is equal to or higher than the appropriate critical value, we will conclude that density of subsequent children mediates the effect of nurse visitation on maternal arterial stiffness. We will use this approach for each hypothesized mediator separately and jointly to develop a map of mediation.

Challenges in the Conduct of This Work

Missing Data. Missing data in this trial have been remarkably low. We are sensitive to the potential pitfalls of analyzing only cases with complete data.¹⁰⁵ We have complete data on all relevant background characteristics, which we will examine to address potential attrition bias. We also will compare our analyses to the same analyses employing inverse proportional weighting. We will perform sensitivity analyses to ensure that results are similar under various assumptions. We will determine whether imputation is valid and has sufficient added value with our data to justify the complexity involved in reporting these analyses.

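### Behaviours and mental state from the 29-year interviews are to be explored as mediators of outcomes measured in the same wave, and nothing in the plan prevents effects of disease on behaviour being read as mediation

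*Combined protocol and SAP*

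**What the plan says.** The section on the approach to Specific Aim Three names two sets of mediators. The hypothesized set (H8, H9) consists mostly of effects from pregnancy to year 18, such as pregnancy-induced hypertension, closely spaced births, mastery, and blood pressure or obesity at years 12 and 18. The second set comes from the current interviews: sedentary and physical activity, sleep, diet, substance use, depression, anxiety, mastery, chronic pain, partner relationships, education, employment, insurance and incarceration. These "will be used as sources of data to explore other potential mediators of NV effects".

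Table 6 of the protocol places most of the second set in the Part 2 face-to-face assessment, alongside anthropometry, arterial measures, blood and urine. Table 5 places tobacco use, education, employment and insurance in the Part 1 telephone interview of the same wave. The Interviews paragraph says that some measures repeat earlier ones, while those of activity, diet and sleep "are new measures appropriate to the life stages of the participants and the outcomes being examined".

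One mediation procedure is given, under Tests of Hypotheses (Hypotheses 8 and 9). The mediator is regressed on treatment, and the outcome is regressed on the mediator within controls. If both paths are significant and z′ reaches a tabulated critical value, mediation is concluded. The text continues: "We will use this approach for each hypothesized mediator separately and jointly to develop a map of mediation". The Statistical Models section describes the purpose of the mediation models as examining causal processes.

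**The concern.** Obesity, hypertension, kidney disease or diabetes present before the 29-year visit can change activity, sleep, mood, pain, work and insurance. If the programme lowers such disease, treatment will predict the behaviour and the behaviour will correlate with the outcome, even if the behaviour has no effect on it. Both paths in the plan's rule can then be significant with a true mediated effect of zero.

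The trial's own tables make this route plausible. Table 3 reports stage 1 hypertension at year 18 in 84.1% of control and 66.3% of nurse-visited mothers of females. Table 4 reports obesity at age 12 in 31.8% of control and 15.9% of nurse-visited female offspring. The arms therefore already differed on disease years before the interview.

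At stake is a causal statement that, for example, the programme improved cardiometabolic health by raising activity or improving mood, when the data fit the opposite direction equally well.

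**Working it through.** **1. The plan's own figure.** The power section assumes "a Type I error of .05, Type II error of .20 (power of .80), 2-tailed tests" and "10 percent of the variance accounted for by other terms in the model for normally distributed variables and N=600", and adds: "Disproportionate sample sizes in Control and Nurse-Visited groups are taken into account". The treatment-condition descriptions give 514 families in Treatment 2 and 228 in Treatment 4.

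- Split of 600: 600 × 514/742 = 416 controls and 184 nurse-visited.
- Smallest detectable effect = (1.960 + 0.842) × √(1/416 + 1/184) × √(1 − 0.10) = 0.235 SD (stated: 0.24).
- The same formula at N=300 gives 0.333 SD (stated: 0.33).

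The stated figures reproduce. The plan gives no figure for the mediation analysis.

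**2. Model of pure reverse causation.** The outcome is Y = d × T + noise, with SD 1 within arm. The behaviour is M = r × Y + noise, scaled to SD 1. M has no effect on Y, so the true mediated effect is zero. Take d = 0.24, the plan's detectable effect. The documents give no correlations, so r = 0.2, 0.3 and 0.5 are assumptions.

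**3. Treatment-to-mediator path.** The arm difference in M is r × d, with standard error √(1/416 + 1/184) = 0.0885. The chance of |z| > 1.96 is Φ(k − 1.96) + Φ(−k − 1.96), where k = r × d / 0.0885.

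**4. Mediator-to-outcome path, controls only.** t ≈ r√414 / √(1 − r²) = 4.15, 6.40 and 11.75, so this path is significant in about 98.6%, 100% and 100% of trials. It offers almost no protection.

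**5. Both paths significant.**

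| r | k | path 1 | path 2 | both |
|---|---|---|---|---|
| 0.2 | 0.542 | 0.084 | 0.986 | 0.083 |
| 0.3 | 0.813 | 0.129 | 1.000 | 0.129 |
| 0.5 | 1.355 | 0.273 | 1.000 | 0.273 |

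Simulation agrees to within about one percentage point. With d = 0 the joint rate is about 5%.

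**6. Adding the z′ step.** The tabulated critical values are not in the documents. As a stand-in, the first-order product z was required to exceed 1.96 as well. By simulation the rates become about 5%, 11% and 26%. With no programme effect they are below 5%.

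**7. Half sample.** At N=300 and 0.33 SD, the setting of H7, the joint rates are about 7%, 12% and 27%.

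**8. Safeguards looked for.** No passage requires the mediator to precede the outcome, fits the reverse model, or adjusts the mediation models for disease at year 18. The Aim One section says that interpretation of outcomes will consider existing disease, but it sets no rule for mediators. Obesity is a candidate covariate in the Statistical Models section, undated and not tied to the mediation models.

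**The case against.** **The decision rule is written for hypothesized mediators.** The current-interview set is only to be explored, and the purpose section says the interviews are there to help interpretation. A reader might infer that mediation will be claimed for these items; the documents do not say so. What stands is narrower: no other mediation method is given for this set, and nothing stops the same conclusion being drawn.

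**Number of tests.** A reader might infer that every candidate is to be tested against every outcome. Aim 3 speaks of selected outcomes, so no such count can be derived.

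**Schedule.** Some items precede the physical measurements, since Part 1 comes before Part 2, or are histories: education, past incarceration, relationship duration, offspring births. The concern is weaker for these, and for deaths after the interview. A short gap does not, however, put current employment, insurance or tobacco use ahead of disease that began years earlier.

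**Size.** The correlations are assumed, the joint step alone overstates the full rule, and at r = 0.2 the excess over the 5% base rate is only about 3 points. That is fair. Pure reverse causation is not an upper bound, though. If the programme has its own 0.24 SD effect on a behaviour that does nothing to disease, and the two correlate only because disease affects behaviour, the first path is significant with probability about Φ(0.24/0.0885 − 1.96) = 77%, and both paths in about 76% to 77% of trials.

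**Earlier disease is already among the mediators.** H8 and H9 include hypertension, prehypertension and obesity at years 12 and 18, to be modelled separately and jointly. That places earlier disease on the mediation map, but it does not make earlier disease an adjustment for the 29-year behaviours. Any ordering drawn in Figures 1 and 2 cannot be checked, because the figures are not reproduced.

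**Earlier waves are not automatically safe.** Stage 1 hypertension was already 63.5% in control mothers of females at year 12, so year-18 behaviour can also follow disease. The earlier mastery and partner data in Table 3 are maternal, and earlier depression, anxiety, pain and insurance measures are not shown. This stands, and it shapes the fix.

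**Conclusion.** The point holds in a limited form. The plan explores same-wave behaviours and mental state as mediators, and its only mediation method cannot separate the two causal directions. A result can therefore be read as mediation with nothing in the plan to prevent it.

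The illustrative size is a joint-significance rate of about 8%, 13% and 27%, or about 5%, 11% and 26% with the product z above 1.96, where the true mediated effect is zero. This rests on N=600 split 416/184, a 0.24 SD programme effect, assumed correlations of 0.2 to 0.5, pure reverse causation, and use of the hypothesized-mediator rule for this set. The rates rise with the programme effect, so the risk is greatest where the programme works best.

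A reader might infer that the main findings are in doubt. They are not: H1-H6 compare randomized groups and do not use these variables. This is a cheap improvement to an exploratory aim.

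**What to change.** In the approach to Specific Aim Three and in the text for Hypotheses 8 and 9:

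1. State that the joint-significance and z′ rule, and any conclusion of mediation, apply only to mediators measured before the outcome.
2. Report the 29-year interview measures as NV-C differences and as concurrent, hypothesis-generating correlates of the outcomes.
3. Where an earlier wave of the same construct exists (for example maternal mastery, substance use or partner status), base any mediation test on that wave. Adjust for disease status measured at or before it, such as blood pressure or obesity at year 12 or 18, because earlier values can also follow earlier disease.

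The cost is plan wording, and step 3 uses data from waves already completed. The loss is that no mediation claim can be made for measures new at this wave, such as activity, diet and sleep. Offspring will also have fewer earlier-wave substitutes than mothers.

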Outcome and Age of Assessment	Sample	Comparison	Nurse	Comp vs. Nurse	
Prenatal/Newborn Health		Mean/Rate	Mean/Rat	p-	Effect size*
Pregnancy-Induced Hypertension, % ¹	Whole-T1+2 vs T3+4	20.0	13.0	.009	OR=0.65
Preterm delivery ¹	Whole	13.3	7.3	.020	OR=0.51
Low birthweight, % ¹	LPR ⁸	19.8	9.5	.010	OR=0.42
High birthweight - %	Mothers of F's	5.3	0.0	.005	Not est
Health behavior index, % – 36 wks. ²	Mothers of F's	67.8	80.2	.038	OR=1.18
Inter-Pregnancy Intervals					
Time to first subsequent birth (0-72 mo.) ³	Whole	30.23	34.38	.01	ES=0.26
Count of closely spaced subsequent births–age 0-12 ⁴	Whole	0.51	0.34	.019	IR=0.67
Maternal Economic & Behavioral Resources					
Count of Substances Used – child age 9	Whole	0.17	0.10	.075	IR=0.62
Role Impairment due to Substance Use–ages 9 & 12	Whole	0.25	0.00	.04	Not est.
Sense of mastery – 36 wks preg to 18 yrs ⁵	Whole	99.62	100.95	.009	ES=0.13
% live with partner – across time ⁶	Whole	32.8	36.8	.09	OR=1.20
% married – across time ⁶	Whole	10.7	14.9	.03	OR=1.37
Public Benefits costs (summed-birth-age 18 yrs) ⁷	Whole	\$192,836	\$175,525	.03	ES=-0.13
Maternal Death over 21-year Period after Birth					
All-cause mortality, %	Whole-T1+T2vs T3+4	3.7	1.3	.008	Not Est.
External-cause mortality, %	Whole-T1+T2vs T3+4	1.7	0.2	.02	Not Est.
Measured Maternal Obesity & Hypertension, and Self-Reported Health Problems – through Child Age 18					
Systolic BP – age 18	Mothers of F's	128.85	123.50	.024	ES=0.30
Diastolic BP – age 18	Mothers of F's	90.03	87.02	.044	ES=0.34
Systolic BP – age 12	Mothers of F's	118.40	112.11	.010	ES=0.31
Diastolic BP – age 12	Mothers of F's	82.51	77.73	.010	ES=0.33
Stage 1 Hyperten (Sys \geq 120 or Dias \geq 80) % – age 18	Mothers of F's	84.1	66.3	.002	OR=0.79
Stage 1 Hyperten (Sys \geq 120 or Dias \geq 80) % – age 12	Mothers of F's	63.5	45.8	.025	OR=0.72
Thyroid Problems (self-report), %- age 18	Whole	6.6	2.6	.030	OR=0.38
Kidney Problems (self-report), % - age 18	Whole	2.5	0.5	.037	OR=0.18
Memory problems (self-report) % - age 18	Mothers of F's	2.1	0.0	.038	Not Est.
High Cholesterol (self-report), % - age 18	Whole	8.3	14.4	.023	OR= 1.87

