Measured Maternal Obesity, Hypertension, and Self-Reported Health Problems. By the first offspring's 18th birthday, nurse-visited (T4) women were less likely to have stage-1 hypertension (at the year 12 and 18 assessments) than women in the control group (T2), effects limited to mothers of females.⁷² In addition, nurse-visited (T4) women reported fewer thyroid problems, kidney problems, and among mothers of females, fewer memory problems.⁷² The presence of hypothyroidism among women with chronic kidney disease increases the risk for serious heart disease.⁷⁷ The one exception to this pattern is that nurse-visited women reported more problems with high cholesterol, an effect essentially limited to those who gave birth to males (not shown).⁷²

Hypothesized Pathways of Program Effects on Maternal Chronic Disease

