H2: Risks for Macrovascular Disease. We will compare NV and C participants on measures of arterial stiffness: peripheral systolic and diastolic BP (averaged over the two assessments), cfPWV, and AI.

H3: Markers of Chronic Kidney Disease (CKD). We will compare NV and C participants on the estimated Glomerular Filtration Rate (eGFR) and the microalbumin/creatinine ratio.

H4: Metabolic Outcomes: We will compare NV and C participants on measures of Glycosylated Hemoglobin (HbA1C), dyslipidemia (TC, LDL, HDL, TG), and the AST/ALT ratio.

H5: Immune/Inflammatory Markers: We will compare NV and C participants on immune/inflammatory markers [hsCRP, fibrinogen, interleukin 6 (IL-6), tumor necrosis factor alpha-receptor 2 (TNF-2), and insulin-like growth factor-1 (IGF-1 – free and total)].

H6: Mortality. We will compare NV and C participants on rates, ages, and causes of death.

The interpretation of outcomes specified in H1-6 will take into consideration the presence of existing disease and disabilities, based upon interviews, records of medication, diagnoses, and hospitalization records.

Approach to Specific Aim Two (Examine Moderators of Intervention Effects)

As elaborated below, we will examine all outcomes in this study in statistical models that employ sex of offspring as a classification factor and maternal psychological resources cross-classified with Treatment condition (NV-C). We have hypothesized (H7) that intervention effects (H1-5) will be more pronounced among females and mothers who gave birth to females, so analyses of NV-C differences will focus on these groups. We have elaborated methods to address this aim under the statistical methods and models below.

Approach to Specific Aim Three (Explore Mediators of NV Effects)

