Hypotheses 1-6 (primary): The NV group is hypothesized to have: H1: lower measures of obesity, (BMI, waist to hip ratios, segmental and % body fat, visceral fat); H2: lower risks for macrovascular disease, reflected in measures of functional arterial stiffness (peripheral BP, cfPWV, AI); H3: fewer markers of CKD - higher eGFR and lower microalbumin/creatinine ratios; H4: better metabolic outcomes (lower levels of HbA1C, TC, HDL, LDLc, TG, AST/ALT ratio); H5: lower levels of immune/inflammatory markers (hsCRP, fibrinogen, IL-6, TNF-alpha receptor 2, IGF-1); and H6: lower mortality rates. We will test Hypotheses 1-5 by examining each of the primary outcomes listed above as dependent variables in our primary T|P|S model, plus covariates from the post-double-selection lasso results. Outcomes also measured at earlier time points will include an additional classification factor for first-born offspring age at assessment (A). We will examine treatment-control difference summing across levels of maternal psychological resources and sex. In addition, we will examine planned contrasts for males and females, and mothers of males and females. Outcomes for hypotheses 1-5 are normally distributed and will be examined in the general linear model or mixed linear model for repeated measure outcomes. Secondary analyses will examine some outcomes in their dichotomous form for those values that cross clinical thresholds (e.g., obesity), which will be analyzed in the logistic model or generalized linear mixed model for repeated measure outcomes.⁹⁰ Hypothesis 6, related to mortality 6, will be examined in survival analysis by treatment condition without additional classification factors consistent with our earlier report on mortality.^{99,69}

Hypotheses 7: NV effects on H1-5 outcomes will be greater for female offspring and mothers who gave birth to females. Planned contrasts in the above aforementioned models for all primary outcomes, with the exception of mortality (given low base rates), will focus on female offspring and mothers of females.

Hypothesis 8: NV effects on maternal outcomes (H1-6) will be mediated, in part, by NV effects on prenatal health behaviors, preterm delivery in first and subsequent births, and PIH in first births; closely spaced subsequent pregnancies, maternal sense of mastery, stable/supportive partnered

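### H4 counts lower HDL as a better outcome, and its transaminase ratio is AST/ALT in the hypothesis but ALT/AST in the laboratory list

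*Combined protocol and SAP*

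**What the plan says.** Under Tests of Hypotheses (Hypotheses 1-6, primary), the metabolic hypothesis is "H4: better metabolic outcomes (lower levels of HbA1C, TC, HDL, LDLc, TG, AST/ALT ratio". The same sentence words the kidney hypothesis as "H3: fewer markers of CKD - higher eGFR and lower microalbumin/creatinine ratios", so it separates a marker expected to rise from one expected to fall.

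The other places that mention these markers give no direction. The specific aims say only that metabolic outcomes will be better. The H4 paragraph under Approach to Addressing Specific Aim One lists "dyslipidemia (TC, LDL, HDL, TG), and the AST/ALT ratio". The Payment for Participation paragraph, which lets participants without a blood sample supply results from the past year's medical records, uses the same list.

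The laboratory list in Methods and Procedures names "ALT/AST ratio (calculation", the ratio the other way up. That list also includes "Chemistry Panel (AST, ALT, Serum Albumin and Serum Creatinine", so both enzymes are assayed individually.

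Three further provisions bear on the point:
- The power section assumes two-tailed tests at .05.
- The Multiple Comparisons paragraph relies on specific hypotheses and coherence across outcomes in place of adjustment.
- The section on reporting untoward effects has analysts log significant effects, or patterns of trends, that run in the unexpected direction, for DSMB review.

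**The concern.** The parenthesis in H4 is what gives 'better' its content, and it places HDL with the markers that should fall. Followed literally, a lower mean HDL in the nurse-visited group supports a primary hypothesis, and a higher mean HDL goes into the log as an unexpected finding.

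Direction matters more here than in many plans. There is no multiplicity adjustment for H1-5, so the reading of results rests on whether effects point the hypothesised way and agree with one another. A wrong sign for one marker corrupts that reading even though the test itself is sound.

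For the ratio, an analyst who takes the laboratory's calculated variable and applies the word 'lower' from H4 is testing the opposite of the stated hypothesis. A second risk lies in data handling. Ratios supplied from medical records are listed as AST/ALT, while the study laboratory's ratio is listed as ALT/AST. Merged as named, one analysis variable would hold values in both orientations.

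**Working it through.** **1. The plan's own design figure.** Inputs: type I error .05 two-tailed, power .80, 10% of variance explained and N=600 (power section); allocation 514 control to 228 nurse-visited (Table 1).

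- Group sizes at N=600: 600 × 514/742 = 415.6 and 600 × 228/742 = 184.4.
- Smallest detectable difference = (1.960 + 0.842) × √[0.90 × (1/415.6 + 1/184.4)] = 2.802 × 0.0839 = 0.235 SD. The plan states .24.
- At N=300 (207.8 and 92.2): 2.802 × √[0.90 × (1/207.8 + 1/92.2)] = 2.802 × 0.1187 = 0.333 SD. The plan states .33.

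Both figures reproduce.

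**2. Does the sign of the HDL hypothesis affect them?** Power at +.24 SD with N=600 is 0.816, and at −.24 SD it is also 0.816. At ±.33 SD with N=300 it is 0.794 either way. A two-tailed test does not use the hypothesised sign, so restating HDL as higher changes no design figure, estimate or p-value.

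**3. H4 directions compared across sections.**

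| Section | HDL | Ratio |
|---|---|---|
| Specific aims | not named | not named |
| Payment for Participation (record-supplied results) | listed, no direction | AST/ALT |
| Laboratory list, Methods and Procedures | listed, no direction | ALT/AST |
| Approach to Aim One, H4 | listed, no direction | AST/ALT |
| Tests of Hypotheses, H4 | lower | AST/ALT, lower |

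HDL is one of six H4 markers. It is given a direction once, that direction is lower, and nothing elsewhere corrects it. The ratio is AST/ALT three times and ALT/AST once.

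**4. What inverting the ratio does.** Let R = AST/ALT and L = ALT/AST = 1/R. For any participant, a lower R is a higher L. The documents give no distribution for the ratio, so the following is an assumed illustration: log-normal values, log-scale SD 0.3, log-scale mean −0.1 in one arm and 0 in the other. The raw mean is exp(μ + σ²/2), with σ²/2 = 0.045.

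- Difference in R: exp(−0.055) − exp(0.045) = 0.946 − 1.046 = −0.10.
- Difference in L: exp(0.145) − exp(0.045) = 1.156 − 1.046 = +0.11.

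The same data meet the H4 wording in one orientation and contradict it in the other.

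**The case against.** The best answer is that the HDL item is a drafting slip and harmless. The governing word is 'better', HDL is listed elsewhere under dyslipidemia, and a metabolic researcher would know what was meant. Much of this stands. It probably is a slip, and no HDL test changes. It does not dispose of the point, because the parenthesis is the only statement of direction, it belongs to a primary hypothesis, and the neighbouring H3 shows that the authors split directions when they meant to.

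The plan also provides for analyses at clinical thresholds, whose cut-offs need not follow the blanket 'lower'. That helps a little. However, Tests of Hypotheses makes these secondary and limits them to some outcomes, with obesity the only example there.

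Some stronger readings are tempting but not supported:

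- A reader might infer that an HDL fall would pass the safety review as a benefit. The monitoring plan has a separate trigger for higher rates of adverse events or outcomes in the nurse-visited groups, and the DSMB reviews the findings for negative side effects. Neither depends on the sign in H4.
- A reader might link this to the excess of self-reported high cholesterol among nurse-visited mothers in Table 3. That item does not separate HDL from other cholesterol, and the text describes the effect as essentially confined to mothers of males. It is no evidence about HDL.
- A reader might infer that the ratio's orientation materially changes the strength of the test. The plan says "Outcomes for hypotheses 1-5 are normally distributed and will be examined in the general linear model" and states no transformation, so inversion on the raw scale need not leave the p-value untouched. The documents give no values from which to size this, and when arms differ by a constant factor the sign simply reverses. Only the ambiguity of direction is claimed here.

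**Conclusion.** The point holds and is minor. One of the six H4 markers has the wrong hypothesised sign as written. A second, the transaminase ratio, is named in two reciprocal orientations, so its direction cannot be applied to the laboratory variable as named.

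The HDL conclusion rests on one assumption from outside the documents: the general convention that higher HDL is favourable. The ratio conclusion needs no outside assumption, because the sections contradict each other. They do not show which orientation was intended.

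The effect on HDL is confined to interpretation: which result supports H4, which agrees with the other outcomes, and which is logged as unexpected. The separate adverse-outcome trigger and the DSMB review partly offset it. For the ratio there is also a practical risk that record-supplied and laboratory values are combined in opposite orientations. The documents do not show that this has happened.

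**What to change.** Before treatment contrasts are examined:

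1. Restate H4 in Tests of Hypotheses as lower HbA1c, TC, LDLc and TG, and higher HDL.
2. Choose one orientation for the transaminase ratio, state its hypothesised direction, and use it in Payment for Participation, the laboratory list, the H4 paragraph under Aim One and Tests of Hypotheses. Compute it from the separately assayed AST and ALT. For results supplied from medical records, note the orientation in which the ratio was reported and convert it to the chosen one.
3. State that the unexpected direction in the untoward-effects log is judged against these corrected directions.

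The cost is a wording change and one derivation rule. Study samples need no new assay, since AST and ALT are both already in the chemistry panel. Record-supplied results need their orientation noted, because the plan names only the ratio for them and the two enzyme values may not be available. Making the change before results are seen also avoids any appearance of choosing a sign afterwards.
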